6.6.4.1 HHIA Ouestionnaire

The 25-item Hearing Handicap Inventory for Adults (HHIA; (Newman *et al.*, 1990)) focuses on the impact of the hearing loss on the subject's daily life and evaluates the change in condition severity after treatment initiation. It is self-administered at FUV3 and FUV4. Response categories for all 25 items are "yes", "no", or "sometimes". The questionnaire is shown in Appendix 3.

6.6.4.2 PGIC scale

The Patient Global Impression of Change (PGIC) scale for hearing loss severity evaluates the change in condition severity after treatment initiation and is administered at FUV2, FUV3 and FUV4. It is shown in Appendix 4.

6.6.4.3 Tinnitus numerical rating scales

The presence or absence of tinnitus and numerical rating scales for subjective tinnitus loudness "at its loudest" ($TLQ_{Loudest}$) and subjective tinnitus annoyance "at its worst" (TAQ_{Worst}) is self-administered at all visits from FUV1 until FUV4, for the $TLQ_{Loudest}$ and TAQ_{Worst} also at TV.

At TV, the presence or absence of tinnitus is assessed by the investigator, using the questionnaire in Appendix 1.

In addition, a subject diary will be used for the subjects to self-record weekly the presence or absence of tinnitus and numerical rating scales. If a subject diary entry is missing within \pm 4 days of a visit, it may be replaced by the visit based values. Subjects will not have access to their previous ratings. Complete remission of ISSNHL-related tinnitus will be given as soon as a subject rates both $TLQ_{Loudest}$ and TAQ_{Worst} as 0, and answers the question about tinnitus presence with "No". Refer to Appendices 1 and 2.

6.6.5 Otologic and audiologic assessments

A detailed description of the trial specific procedures for otologic and audiologic assessments will be provided to all trial sites.

6.6.5.1 Otoscopy or microscopy

Otoscopy or microscopy will be performed to ensure that the ear canal of the affected ear is clear and to check for the presence of any relevant otologic disease or abnormality such as otitis media, myringitis, or tympanic membrane perforation. It will be performed with an otoscope or ear microscope and appropriately sized speculum that best fits the ear canal. Otoscopy or microscopy will be performed at each visit.

6.6.5.2 Tympanometry

Tympanometry will be performed to check for the presence of otitis media or Eustachian tube dysfunction. It will be performed at TV and, provided the tympanic membrane is closed, also at all follow-up visits starting at FUV2.

Tympanic peak pressure pass is between +25 daPa and -160 daPa. Maximum compliance pass is between 0.3 and 1.4 mL. For further details refer to the corresponding manual.

6.6.5.3 Pure tone audiometry

Air and bone conduction hearing thresholds will be tested at all visits (excluding cFUV).

All tests will be performed by certified audiologists or adequately trained site staff and conducted in a sound attenuated booth/room with doors closed, using standard earphones or earphone inserts.

Compliance with relevant standards will be verified and documented during source data verification. In order to assure overall quality and consistency, individual or all pure tone audiometry data may be reviewed by an independent expert designated by the Sponsor.

Timing of Baseline Assessment

Results of audiograms previously performed as part of routine clinical practice at the investigational site should not be older than 2 hours prior to signing the ICF, and 5 hours prior to the IMP administration (i.e. study treatment must be done within 5 hours from pure tone audiometry) to be considered valid for baseline, otherwise the measures have to be repeated. Pure tone audiograms performed for subjects presenting within the first 24 hours from ISSNHL onset have to be confirmed by a new assessment that is conducted at the earliest 24 hours after onset of ISSNHL. The high possibility of spontaneous remission early after ISSNHL onset may otherwise lead to the inclusion of patients who would recover on their own. The new confirmatory measure will serve as baseline value.

Assessment of Hearing Thresholds

Hearing thresholds will be determined by pure tone audiometry in both ears at 0.25, 0.5, 1, 2, 3, 4, 6, and 8 kHz (air conduction), and at 0.5, 1, 2, 3, 4 kHz (bone conduction) in accordance with ISO standard 8253-1 and any other relevant standards.

For each frequency, hearing threshold is to be determined by (A) approaching the hearing threshold in 20 dB steps, followed by (B) fine tuning steps in 5 dB steps or smaller. Fine tuning determination occurs by detecting, at least twice, the level at which the subject no longer hears the tone and the level at which the subject starts to hear the tone. The hearing threshold is defined as the lowest tone level at which the test subject hears the tone, and which is confirmed by a second measure.

Determination of the three most affected contiguous frequencies

At baseline, the three most affected contiguous frequencies which are used for the calculation of Pure Tone Average (PTA) are defined relative to the reference values which is either the unaffected contralateral ear or, in case of asymmetric hearing, corresponding values from a pre-existing audiogram for the affected ear not older than 2 years.

For the evaluation of the eligibility of the subject, the three most affected contiguous air conduction audiometric pure tone frequencies are used. These represent the frequencies with the highest hearing loss (defined as difference to the reference values). The determination of the hearing loss is done as follows:

1. For each frequency the difference between the hearing threshold of the affected ear and the hearing threshold of the reference (i.e. unaffected contralateral ear or in case of asymmetric

- hearing in medical history: pre-existing audiogram not older than 2 years) is calculated (subtract hearing threshold_{affected} ear from the reference value (e.g. hearing threshold_{unaffected ear}).
- 2. The three contiguous frequencies with the highest absolute hearing loss (i.e. hearing loss difference) values are used to calculate the average hearing loss (inclusion criterion no. 3).
- 3. If the average hearing loss is the same across different sets of frequencies the set of lower contiguous frequencies is used.
- 4. The same frequencies are used to calculate the average hearing threshold to evaluate if inclusion criterion no. 2 is met.

Further details are provided in the corresponding manual.

The pure tone average frequencies are determined from the pure tone audiometry (air) at baseline and are fixed throughout the trial, to evaluate hearing improvement. If for any post-baseline assessment, a measurement of one of the three PTA frequencies is missing, the average of the available 2 most affected frequencies is still considered valid.

6.6.5.4 Speech audiometry

The speech discrimination (Word Recognition Score in quiet) will be determined in both ears with country-/language-specific word lists at 60 and 80 dB sound pressure level (SPL). WRS at both stimulus levels (WRS $_{(60 \text{ dB})}$) and WRS $_{(80 \text{ dB})}$) will be determined, at the earliest, 24 hours after ISSNHL onset and this result will serve as baseline value.

When testing, at each stimulus level, 40 to 50 mono- or bisyllabic words from language-specific standard lists (e.g. CID-W22 for American English and Auditec Spanish BiSyllable Word Recognition test in U.S.) without background noise will be presented in random order from a recorded source. Full lists are to be used. After each word is presented to the subject, the subject will be asked to repeat it, and to guess it if he/she is not sure of the word. The testing will start with the unaffected ear. The WRS will be calculated (as the percentage of correct responses) for each ear.

Speech audiometry at 80 dB will be performed at all trial visits (excluding cFUV) for both ears. WRS at 60 dB will be performed at TV and FUV4 only. Results of previously performed speech audiometry tests performed at the investigational site should not be older than 2 hours prior signing the ICF and 5 hours prior to IMP administration (i.e. study treatment must be done within 5 hours from speech audiometry) to be considered valid for baseline, otherwise the measurements have to be repeated.

6.6.6 Vestibular function

A detailed description of the trial specific procedures for assessment of vestibular function will be provided to all trial sites in the corresponding manual. Vestibular function will be assessed by means of Romberg's test and Frenzel goggles, at the earliest, 24 hours after ISSNHL onset and this result will serve as baseline value.

6.6.6.1 Spontaneous nystagmus

The number of spontaneous nystagmus beats is measured with Frenzel goggles. The assessment is performed in a darkened room and involves a thorough examination of the eye movements to check if the movements are conjugate. Spontaneous nystagmus beats will be recorded for 30 seconds and documented with the direction of beat. The exam will be performed at each visit (excluding cFUV). Observation of > 10 beats / 30 seconds is considered clinically relevant.

The test may also be performed by videonystagmography (VNG).

6.6.6.2 Balance test

Romberg's test (balance test) will be performed at each trial visit (excluding cFUV).

The essential features of the test are as follows:

- 1. The subject stands with feet together, eyes open and hands by the sides.
- 2. The subject closes the eyes while the Investigator, or designee, observes for a full minute.

During the test the Investigator, or designee, stands close by as a precaution in order to stop the subject from falling over and hurting himself or herself.

Romberg's test is positive if the patient sways or falls. The result of the test is to be recorded.

6.6.7 Suicidality

Suicidality (suicidal ideation and behavior) will be assessed by means of the C-SSRS by a study team member that has been trained and certified according to the requirements. A clinical training or medical degree is not required for the rater as the questionnaire is designed for suicide risk identification in a wide range of settings by lay persons who have completed the required training. The C-SSRS is shown in Appendix 5. The C-SSRS will be assessed at TV (Baseline version), FUV2, FUV3 and FUV4 (Since-Last-Visit version).

6.7 Randomization

Once all procedures at TV have been performed (i.e. all baseline and safety assessments as described in sections 6.5 and 6.6) and the subject has been confirmed to be eligible for the trial the Investigator, or designee, will randomize the subject using an Interactive Web Response System (IWRS).

Subjects will be randomized to receive either AM-111 (0.4 mg/mL or 0.8 mg/mL) or placebo in a 1:1:1 ratio.

At the time of randomization, the IWRS will assign the subject a unique IMP kit number; details are described in the corresponding manual.

6.8 IMP administration

Trial subjects will have the tympanic membrane of the treatment ear topically anesthetized as per standard practice at the respective site and then receive an intratympanic administration of the IMP (AM-111 0.4 mg/mL, AM-111 0.8 mg/mL or placebo) as assigned by IWRS.

For the application procedure, trial subjects are to sit on a reclined ear nose throat (ENT) exam chair or lie supine on an examination couch. The head is placed in a position tilted approximately 45° towards the non-treated contralateral ear, so that the ear to be treated is pointing upwards. Following cleaning of the ear canal, a local anesthetic is applied topically onto the eardrum. The local anesthetic may be chosen by the Investigator as per local practice (e.g. lidocaine) and must be recorded in the source documents and on the CRF. The use of phenol is discouraged, as it may lead to slower healing of the tympanic membrane. Upon induction of anesthesia and prior to the administration of the IMP, any remaining anesthetic must be carefully and gently (avoiding loud noise) suctioned off from the ear canal.

For the intratympanic administration, the IMP is supplied in pre-filled syringes with a luer lock. At the Investigator's discretion either a spinal needle or a micro suction tube may be used; the choice of injection cannula must be recorded in the source documents and on the CRF. Prior to the administration, the drug must be warmed up gently to about body temperature (e.g. by hand-warming) to prevent caloric vertigo.

The administration is performed preferably in the posterior-inferior quadrant (left ear: about 3 o'clock, right ear about 9 o'clock), preferably close to the limbus. Alternatively, the administration may be performed in the anterior-inferior quadrant; the choice needs to be documented in the source documents and on the CRF. At the Investigator's discretion, the tympanic membrane may be punctured with the needle for injection (tympanopunction) or a small myringotomy may be performed first; in this case the needle will penetrate through the incision. If deemed necessary, at the Investigator's discretion, an outlet for displaced air may be created through a second tympanopunction or myringotomy superior to the first one. The choice of the approach is to be noted in the source documents and in the CRF.

the IMP is gently injected into the middle ear. Following IMP administration, trial subjects remain in their position for 30 minutes to allow for diffusion of the active substance across the RWM. Subjects are asked to refrain from movements of the head, swallowing, yawning, sneezing or talking during the resting period, if possible. The timing of the IMP administration is to be documented in the source documents and on the CRF. The syringe is to be kept for drug accountability, as per country specific requirements documented in the operations manual.

For a more detailed description of the IMP administration procedure please refer to the instructions included in the Operations Manual.

6.9 Background therapy administration

As background therapy, an oral corticosteroid course will be offered for 14 days followed by a 5-day taper as follows (in line with clinical practice guidelines for sudden hearing loss (Stachler et al., 2012):

- Prednisone or Prednisolone at 1 mg/kg/day, at a maximum 60 mg/day (taper 50 mg, 40 mg, 30 mg, 20 mg, and to 10 mg), or
- Methylprednisolone at 0.8 mg/kg/day, at a maximum 48 mg/day (taper 40 mg, 32 mg, 24 mg, 16 mg, and to 8 mg).

The dose should be adjusted to the next available strength. It is to be taken undivided in the morning and can be started within 36 hours prior to randomization. If the course is started within 36 hours prior to randomization, the maximum dose will be given from Day -2 until Day 12. If the course is started on TV, the maximum dose will be given until Day 13.

The background corticosteroid treatment may be omitted in case of medical contraindication of oral corticosteroids or if declined by the subject.

Corticosteroids should not be administered to patients with the following conditions:

- Hypersensitivity to any ingredients in the formulation.
- Systemic infections unless specific anti-infective therapy is employed.
- Ocular herpes simplex due to the possibility of perforation.
- Medical conditions which can be affected by corticosteroids, such as insulin-dependent or uncontrolled diabetes mellitus, tuberculosis, peptic ulcer, etc.

Treatment compliance is to be documented by the subject on a background therapy documentation card and will be verified by the Investigator. All used and/or unused packaging has to be returned by the subject to the site. Further details are provided in Section 8.45.

7 Trial visits and schedule of assessments

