7.1 Baseline assessment, randomization and treatment

After having obtained informed consent from the subject, the baseline assessment begins at the treatment visit (TV) prior to randomization and IMP administration. It ends once all pre-randomization assessments have been completed. No trial specific procedure must be performed before the subject and the Investigator, or designee, have signed and dated the ICF. Signing the ICF defines the start of the trial. The time of signing the ICF and of the baseline assessments should be recorded in the source documents and on the CRF. Please refer to section 6.3 for details on timing of baseline assessments.

The required procedures may be done on different calendar days, however the day of randomization and treatment (IMP administration) is considered Day 0 (D0).

After ICF signature and prior to randomization, the following baseline assessments will be performed:

- Inclusion and exclusion criteria qualification (see 6.5.1.);
- Demography/baseline characteristics;
- Medical history;
- Hearing loss onset;
- Prior and concomitant medication;
- Tinnitus evaluation (history and characteristics);
- General physical examination, body weight, height;
- Vital signs (blood pressure, temperature, pulse);
- Tinnitus presence or absence and numerical rating scales;
- Otoscopy/microscopy;
- Tympanometry;
- Pure tone audiometry (air and bone conducted)*;
- Speech audiometry $(WRS_{(80 \text{ dB})} \text{ and } WRS_{(60 \text{ dB})})^{**}$;
- Spontaneous nystagmus (Frenzel goggles)**;
- Balance test (Romberg's test)**;
- Suicidality questionnaire (C-SSRS, Baseline version);
- Blood sampling for laboratory assessment (hematology, biochemistry, virology);
- Urine pregnancy test, if applicable;
- Adverse event reporting.

Prior to randomization, results of all baseline assessments (except hematology, biochemistry and virology results, which will become available only later) will be reviewed. Subjects who do not meet all inclusion criteria and / or who meet one or more of the exclusion criteria are excluded at this point and will not be randomized (screening failures).

Eligible subjects are randomly allocated to either the active treatment (AM-111 0.4 or 0.8 mg/mL) or placebo.

After receiving the single dose of IMP, all subjects will be advised to avoid noisy situations until FUV4, and to protect the ear canal and middle ear of the treated ear from water exposure until the tympanic membrane is closed again.

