8.2.4 Background therapy

The background therapy (corticosteroid) is self-administered by eligible and consenting subjects for 14 days followed by a 5-day taper, starting on TV (or at the earliest within 36 hours prior to randomization). The background therapy consists of an oral corticosteroid course with prednisolone or methylprednisolone as follows:

- Prednisone or prednisolone 1 mg/kg/day, at a maximum 60 mg/day (taper 50 mg, 40 mg, 30 mg, 20 mg, and to 10 mg), or
- Methylprednisolone 0.8 mg/kg/day, at a maximum 48 mg/day (taper 40 mg, 32 mg, 24 mg, 16 mg, and to 8 mg).

The dose is to be adapted to the next strength available and to be taken undivided in the morning and can be started within 36 hours prior to randomization. If the course is started within 36 hours prior to randomization, the maximum dose will be given from Day -2 until Day 12. If the course is started on TV, the maximum dose will be given until Day 13.

The background corticosteroid treatment may be omitted in case of medical contraindication of oral corticosteroids or if declined by the subject. The investigator will provide a background therapy documentation card for the subject to document the intake of the corticosteroid.

Procurement of the background therapy will be performed by the hospital / site directly.

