4.4 ADMINISTRATION OF STUDY MEDICATION

Trial subjects will receive an intratympanic administration of the IMP (AM-111 0.4 mg/mL, AM-111 0.8 mg/mL or placebo) as assigned by the IMP is gently injected into the middle ear. The timing of the IMP administration is to be documented in the source documents and on the case report form (CRF).

Subjects will also receive a course of oral corticosteroids for 14 days followed by a 5-day taper unless medically contraindicated or declined by the subject. This corticosteroid therapy is not mandatory. The intake of the corticosteroid therapy has to be recorded by the subject on a background therapy documentation card.

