7.2 KEY DEFINITIONS

Baseline:

Baseline is defined as pre-intratympanic administration assessment or baseline is the last non-missing assessment value before the first dose of study IMP. This definition will be used for all baseline and change from baseline analyses, unless specified otherwise.

Pure tone audiograms measured in subjects presenting within the first 24 hours from ISSNHL onset have to be confirmed by a second measure that is conducted, at the earliest, 24 hours after the onset of ISSNHL. This new confirmatory assessment will serve as baseline value.

Speech audiometry, spontaneous nystagmus and balance test will be assessed, at the earliest, 24 hours after ISSNHL onset, and this measurement will serve as baseline value.

First Dose Date:

For subjects randomized to AM-111, the first dose date will be defined as the date of TV Day 0.

Study Day:

Study day is defined as the number of days from the date of first dose to the event/visit date. It is calculated as follows: Study Day = Event or Visit Date - First Dose Date.

Hence, the date of first dose is referred to as Day 0. The previous day is Day -1.

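### SAP 8.4.1 puts the limit for an early corticosteroid start at 24 hours where the protocol and the rest of the SAP say 36; as a lesser point, the protocol's early-start day range counts to 15 days, not 14

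*Protocol*

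**What the plan says.** **Start limit.** Protocol 6.9 says of the corticosteroid dose: "It is to be taken undivided in the morning and can be started within 36 hours prior to randomization". The protocol mentions the 36-hour limit ten times: twice in the Protocol Summary (exclusion criterion 14 and the background-treatment row), once in 5.2 (exclusion criterion 14), twice in 6.9, three times in 8.2.4, and once each in 8.6 and 14.4. The SAP gives 36 hours in 4.1.2 (exclusion criterion 14) and in 4.3. SAP 8.4.1 carries over the list of barred treatments from Protocol 8.6, but there the exception for background therapy has a limit of 24 hours.

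**Length of the course.** Protocol 6.9 sets the duration: "As background therapy, an oral corticosteroid course will be offered for 14 days followed by a 5-day taper". SAP 4.4 agrees: "a course of oral corticosteroids for 14 days followed by a 5-day taper". Protocol 6.9 then gives day labels for an early start: "If the course is started within 36 hours prior to randomization, the maximum dose will be given from Day -2 until Day 12". Protocol 8.2.4 repeats that range ("the maximum dose will be given from Day -2 until Day 12") and gives the other case: "If the course is started on TV, the maximum dose will be given until Day 13". Protocol 7.1 makes the day of randomization and treatment Day 0, and SAP 7.2 adds: "The previous day is Day -1".

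**The concern.** The 24-hour figure matters because SAP 8.4.1 is the SAP's only list of treatments barred during the trial. SAP 6.5 has deviation categories for prohibited medication and for background therapy, and SAP 6.3 names forbidden concomitant medication as a possible major violation. A programmer or data reviewer who follows 8.4.1 literally could flag a subject who met every protocol rule. That flag could then be raised when the Per Protocol set is decided. The set feeds two descriptive tables: 14.2.1.2 (PTA) and 14.2.2.2 (WRS at 80 dB).

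The day range is a separate and smaller matter. The printed labels do not agree with the 14-day course in the same section, so a site following them to the letter would give one full-dose day too many.

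**Working it through.** **1. The start limit, side by side.**

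| Document | Where | Mentions | Limit |
|---|---|---|---|
| Protocol | Summary 2, 5.2 1, 6.9 2, 8.2.4 3, 8.6 1, 14.4 1 | 2+1+2+3+1+1 = 10 | 36 h |
| SAP | 4.1.2 1, 4.3 1 | 2 | 36 h |
| SAP | 8.4.1 | 1 | 24 h |

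Twelve mentions stand against one. The sentences in Protocol 8.6 and SAP 8.4.1 differ only in the number. The list of changes from the protocol in SAP section 12 does not mention the limit.

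**2. Who falls between the two limits.** Let t be the clock time of the first steroid dose and r the clock time of randomization on Day 0.

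- First dose on Day -1: gap = 24 + (r - t) hours. It exceeds 24 but not 36 when t < r ≤ t + 12. Example: dose at 08:00, randomization at 14:00, gap = 24 + (14 - 8) = 30 h. With morning dosing this is an ordinary case.
- First dose on Day -2: gap = 48 + (r - t) hours, which always exceeds 24. It is at most 36 only when t ≥ r + 12, so the dose must be at noon or later and randomization before noon. Example: dose at 20:00, randomization at 08:00, gap = 48 + (8 - 20) = 36 h.

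**3. How many subjects.** The documents do not say. SAP section 4 reports 56 enrolled, and Protocol 5.3.1 counts screening failures as enrolled, so the range is 0 to at most 56. If the arms are equal (an assumption), 56/3 = 18.7 per arm at most, and one exclusion removes at least 1/18.7 = 5.4% of an arm.

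**4. The length of the full-dose course.** Inclusive count = last day - first day + 1.

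- TV start, Day 0 to 13: 13 - 0 + 1 = 14. This reproduces the stated duration.
- Early start as printed, Day -2 to 12: 12 - (-2) + 1 = 15.
- Reading the end day as excluded: 13 - 0 = 13 and 12 - (-2) = 14. Numbering without a Day 0 also gives 13 and 14.

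No single convention makes both ranges 14. Under the inclusive count, two ranges would restore it: Day -1 to 12 (12 + 1 + 1 = 14) and Day -2 to 11 (11 + 2 + 1 = 14).

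**5. Size of the extra day at the dose cap.**

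- Prednisone or prednisolone, taper 50+40+30+20+10 = 150 mg: 14 × 60 + 150 = 990 mg; 15 × 60 + 150 = 1050 mg; 60/990 = +6.1%.
- Methylprednisolone, taper 40+32+24+16+8 = 120 mg: 14 × 48 + 120 = 792 mg; 15 × 48 + 120 = 840 mg; 48/792 = +6.1%.

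**The case against.** The best defence is that SAP 8.4.1 is mostly restated protocol text. Its only analysis instruction is a by-subject listing of other therapies. Deviations are departures from the protocol, and the protocol says 36 hours everywhere, so a 24-to-36-hour starter has broken no rule. The last item of the same SAP list excepts background therapy with no time limit at all. Exclusion from the Per Protocol set also needs a major deviation that would interfere with the primary or main secondary analysis, and SAP 6.3 leaves room for discussion at the Blind Data Review Meeting. All of this stands, and it keeps the point minor. It does not make the number right: the SAP still contradicts its parent protocol and two of its own sections.

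On the day range, a reader might infer that Day -1 is simply the correct label. Much favours it: it gives 14 days, it explains why the end moves from Day 13 to Day 12, and a morning dose on Day -2 is always more than 36 hours before any time on Day 0. But the window is defined in hours, and exclusion criterion 14 sets no clock time for steroid already begun. An afternoon or evening start on Day -2 can qualify, as step 2 shows, and would then need to end on Day 11. The documents do not settle which label is wrong.

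A reader might also infer that 24 hours is left over from an older protocol, since SAP section 2 names protocol Version 3.0 and the SAP reference list cites Version 2.0. That is plausible, but nothing in the documents shows what Version 2.0 said.

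**Conclusion.** The 24-hour limit in SAP 8.4.1 is wrong as written and should be corrected; the severity is minor. A reader might infer that compliant subjects will be dropped and the Per Protocol results distorted. The documents do not support that: no subject is shown to have started 24 to 36 hours before randomization, exclusion would not be automatic, and the tables concerned are descriptive only. The figure of about 5% of an arm per exclusion rests on equal arms and on an exclusion actually being made. The Efficacy Analysis Set summaries and the sample size depend on neither point.

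The day range is an internal inconsistency of one day. Its practical reach is small: starts on Day -1 or on TV already end on the right day under the printed text, the therapy is optional, and Protocol 4.2 expects no effect from corticosteroids. Recruitment stopped on 28 November 2017, so corrected protocol wording cannot alter any dose already taken.

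**What to change.** In SAP 8.4.1, replace 24 hours with 36 hours, preferably before deviations are classified at the Blind Data Review Meeting. This is the only part that can still affect the trial. It costs one number and needs no new data, because Protocol 14.4 already has pre-randomization corticosteroid use noted on the documentation card.

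For consistency, replace the day range in Protocol 6.9 and 8.2.4 with a rule: 14 consecutive full-dose days counted from the actual first dose, then the 5-day taper. Day -1 to Day 12 and Day 0 to Day 13 can be given as examples, not as the definition, so that a qualifying late start on Day -2 (ending on Day 11) is also covered. This costs one phrase in each of two sections.
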